## 1. Background and significance

Complications that occur in laparoscopic surgery are often associated with the initial entry into the peritoneal cavity. The literature reported incidences of Veress Needle (VN) injuries of e.g. 0.31% and 0.23%. In a 2010 national survey of laparoscopic entry techniques in the Canadian General Surgical practice, 57.3% of respondents had either experienced or witnessed a serious laparoscopic entry complication like bowel perforation and vascular injury. As those complications are potentially life threatening and should be avoided at all costs, improving safety of this initial action is paramount.

Based on a bare minimum design approach with focus on function expansion of existing components, a new Safety mechanism was developed for the VN that decreases the risks of VN overshooting. The mechanism works by preventing the puncturing acceleration of the tip of the VN by decoupling the surgeon's hand from the VN immediately after entering the abdomen.

A first prototype of our so called VN+ with force decoupling mechanism proved very reliable in reducing overshooting in an ex-vivo model.

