## 2. Study objective(s):

The purpose of the study is to repeat our previous ex-vivo experiments in a real-life laparoscopic set up in a human/cadaveric model.

The primary objective will be to establish what the amount of benefit will be in using the VN+ as compared to a standard VN. We need to measure in a life-like situation what the reduction of the overshoot will be while in the hands of novices, junior residents and experts to validate the learning curve. Other secondary objectives are establishing the amount of haptic feedback of the VN+ compared to the standard VN and potential safety issues. All the practical investigations will need to take place in the ASC. Data study and technical alterations on the instruments will take place at the TU Delft.

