#### 4. Data collection and analysis

In all three groups the measured maximum insertion depths will be calculated in Excel and then any differences between the conventional (VN) and the modified (VN+) groups will be determined with a Mann-Whitney test (SPSS v16, SPSS inc. Chicago, IL) as the data will not be normally distributed. A p-value<0.05 will be considered significant.

All inadvertent tissue or organ damage will be determined and compared between the two types of needles and the groups using a Student T-test (SPSS v16, SPSS inc. Chicago, IL).

A questionnaire (with a Likert scale) will be used to establish the amount of haptic feedback the subjects experience with either the VN or the VN+ at the two different entry sites.

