#### 7. Ethical Considerations

If the VN+ really does make a significant difference in safety of VN insertion its use will lead to a worldwide reduction in morbidity and mortality caused by VN insertion. A pilot study in an ex-vivo animal (pig) model showed significant positive results. In order to take the step to clinical implementation experiments on human tissue are paramount.

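### The primary objective is the size of the reduction in overshoot, but for insertion depth the plan specifies only an unpaired Mann-Whitney p-value, with no estimate or interval

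*Combined protocol and SAP*

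**What the plan says.** Section 2 states an estimation aim: "The primary objective will be to establish what the amount of benefit will be in using the VN+ as compared to a standard VN". It adds that the study must measure "what the reduction of the overshoot will be while in the hands of novices, junior residents and experts to validate the learning curve".

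Section 3.1 describes a crossover in three groups of 10 (novices, residents, experts). Device order is randomised, and each participant makes five attempts with one device and then five with the other. Section 3.2 measures depth by counting engraved marks visible in the abdomen, and gives a total of 300 insertions.

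Section 4 covers the depth analysis in two sentences: "In all three groups the measured maximum insertion depths will be calculated in Excel", after which "any differences between the conventional (VN) and the modified (VN+) groups will be determined with a Mann-Whitney test", and "A p-value<0.05 will be considered significant". No other section adds a summary statistic, a contrast or an interval. The experience groups are compared explicitly only for tissue or organ damage, which is to be "compared between the two types of needles and the groups using a Student T-test".

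On earlier evidence, section 1 says that the prototype "proved very reliable in reducing overshooting in an ex-vivo model", and section 7 says: "A pilot study in an ex-vivo animal (pig) model showed significant positive results".

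**The concern.** The objective asks how much, and the analysis answers whether. A Mann-Whitney p-value depends on ranks alone, so a small consistent reduction and a large one can give the same result. Earlier ex-vivo work is already reported as positive, so a large part of what a cadaver study can add is the amount of the reduction in a life-like setting, with its uncertainty. If the statistic is not fixed in advance, the choice between mean, median or percentage, and between pooled and per-group results, is left until the data have been seen.

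The test also treats the two devices as separate samples, although the same 30 people supply both. This could act in either direction. People who push deep with both needles add variation that a paired analysis would remove. Counting five attempts by one person as five independent results would overstate the information. The plan states neither the unit of analysis nor any variance, so the net effect cannot be determined.

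The same gap affects experience, to a lesser degree. Section 2 wants the reduction in each group, and section 4 names no estimate for any group.

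**Working it through.** **1. The plan's own count.** From section 3.1: 3 groups × 10 participants × 2 devices × 5 attempts = 300, which matches section 3.2. That is 150 insertions per device overall and 50 per device in each group. The plan gives no other figure to reproduce: there is no SD, effect size, power or sample-size calculation.

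**2. What is named for depth.**

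| Item | Asked for in section 2 | Named in section 4 |
|---|---|---|
| Overall VN v VN+ | Size of benefit | Test and p-value only |
| Each experience group | Reduction in each | No estimate or interval |
| Reduction compared between groups | Implied by the learning-curve aim | Nothing for depth |

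**3. What the planned test can return.** Suppose mark counts within each device run from 0 to 5 (an assumption for illustration).
- VN shifted by 6 marks: VN runs 6 to 11, so every VN value exceeds every VN+ value, and U = 150 × 150 = 22,500.
- VN shifted by 12 marks: VN runs 12 to 17, and U is again 22,500. The ties are unchanged, so p is the same.
- Within one group the same holds at U = 50 × 50 = 2,500.

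A second check used simulated depths, 150 v 150. Multiplying every depth by 5 left p at 8.7 × 10⁻⁸, while the median pairwise difference rose from 2.4 to 12.1 units.

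**4. Per-group tests do not compare groups.** Section 4 may mean one test in each group. If experience were then judged by which tests are significant, an identical true benefit would look mixed with probability 1 − p³ − (1 − p)³, where p is the power in each group and the tests are independent. At an assumed p of 0.8 this is 1 − 0.512 − 0.008 = 0.48; at 0.5 it is 0.75 and at 0.9 it is 0.27. The plan does not say it will reason this way, so these are not its error rates.

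**5. Precision available from the planned data.** Let s be the SD of participant differences (mean VN minus mean VN+). The t-based 95% half-widths are:
- 30 participants: 2.045/√30 = 0.373 s
- one group of 10: 2.262/√10 = 0.715 s
- two groups of 10 compared: 2.101 × √(2/10) = 0.940 s (18 df), or 2.052 × √(2/10) = 0.918 s with variance pooled over three groups (27 df)

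Mean half-widths of the exact rank-based (Hodges-Lehmann) interval, from 6,000 simulated samples per distribution:

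| Comparison | Normal data | Range over six assumed shapes |
|---|---|---|
| 30 participants | 0.38 s | 0.30 to 0.40 s |
| One group of 10 | 0.71 s | 0.65 to 0.75 s |
| Two groups of 10 compared | 0.99 s | 0.70 to 1.04 s |

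**6. Cadavers.** Section 3.2 expects about three: 300/3 = 100 insertions each. One experience group also makes 10 × 10 = 100. The plan does not say how cadavers are allocated. If each group had its own, experience and cadaver could not be separated.

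**The case against.** The strongest defence is that testing for a difference is itself an aim. Section 2 opens by describing a repeat of the ex-vivo experiments in a human cadaveric model, the pilot was in pig tissue, and section 7 asks whether the device makes a significant difference. This stands: the planned test is relevant, apart from its neglect of pairing. A reader might infer that the plan cannot meet its primary objective at all. The documents do not support that, because depth is recorded for every insertion and the estimate could still be computed from the planned data.

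It can also be said that section 2 names the quantity (reduction of overshoot) and section 3.2 the measurement (marks), and that the spreadsheet calculation may include summaries by device and group. That is fair, and it narrows the gap to the statistic and its interval. It does not close the gap, since the spreadsheet sentence names no contrast and no measure of uncertainty.

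On experience, a reader might infer that the plan promises a formal comparison of benefit between groups and then omits it. Section 2 asks for the reduction in each group and only implies a comparison. It also leaves unclear whether the experience question is primary or secondary. The comparison between groups in section 4 concerns tissue damage, so it neither fills this gap nor shows that a depth comparison was intended.

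**Conclusion.** The point holds. For the primary objective, the plan names no estimate and no interval for depth, and its one planned inference is a rank test that cannot distinguish a 6-mark from a 12-mark shift once the devices separate. That test is also unpaired in a design where every participant uses both devices. The missing estimates by experience group are part of the same gap. The missing comparison between groups is a lesser, secondary matter.

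The conclusion about missing items rests on the text alone. The rank illustration assumes mark counts of 0 to 5 within a device. The half-widths assume independent participants, which shared cadavers may weaken, and they are in SD units because the documents give no SD. No figure in mm can be stated.

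**What to change.** In section 4:

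1. For each participant, compute mean VN depth minus mean VN+ depth over the five attempts per device. Fix one rule for entry site in advance: section 3.2 names two sites, and five attempts cannot be split equally between them.
2. Report the overall reduction across the 30 participants as a Hodges-Lehmann estimate with 95% CI, converted to mm from the mark count and a stated mark spacing. Replace the Mann-Whitney test with the Wilcoxon signed-rank test. Making the pooled result primary is a proposed choice: the primary-objective sentence names no group, and 30 participants give about half the interval width of 10.
3. Report the same estimate and 95% CI in each experience group.
4. As secondary and exploratory, report differences in the reduction between groups with 95% CIs, so that this question too gets more than a p-value. State that a non-significant result will not be read as equal benefit.
5. Record site, device order and cadaver for each insertion, and run a sensitivity analysis for period and cadaver. If cadaver and experience group coincide, say in the report that they cannot be separated.

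The cost is new wording in section 4, a little more analysis, and three extra fields per insertion, which must be in place before the first session. No participants or insertions are added. Two limits remain. The experience comparison will be imprecise, at about ±1.0 SD of participant differences between two groups. The Hodges-Lehmann estimate is a pseudomedian, which differs from the mean if the differences are skewed.

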### 3.2 Procedure and anatomical considerations

After making a small skin incision the insertion of the Veress needles will be:

- at Palmer's point which is 2-3 cm below the left costal margin in the midclavicular line.
- right below the umbilicus after lifting the skin with a clamp

A "grid" will be drawn on the skin. Guided by the grid each attempt will be in a new and unused part of the abdominal wall.

As in total 300 VN(+) insertions have to be performed we will probably need three cadavers

The anatomical region to be used will thus be the abdomen.

In order to see what depth the different needles reach and the possible anatomical structures that will be injured, we will first introduce a laparoscope in the left (or depending on the cadaver the right) lower abdominal quadrant via an open technique and establish pneumoperitoneum through this laparoscope trocar with a pressure that is as low as possible.

Then measurements will take place through recording the number of marks on the needle (previously laser engraved) that are to be seen in the abdomen. The actions will all be filmed and photographed.

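### The only planned depth analysis is a rank test, which gives no size for the overshoot reduction and does not by itself show fewer deep insertions

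*Combined protocol and SAP*

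**What the plan says.** Section 2 asks for a size: the study must measure "what the reduction of the overshoot will be while in the hands of novices, junior residents and experts". Section 1 gives the reason: "a new Safety mechanism was developed for the VN that decreases the risks of VN overshooting". It cites VN injury incidences of 0.31% and 0.23%, and says of entry complications: "As those complications are potentially life threatening and should be avoided at all costs, improving safety of this initial action is paramount".

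Depth is obtained by "recording the number of marks on the needle (previously laser engraved) that are to be seen in the abdomen" (section 3.2). For the analysis, section 4 says "In all three groups the measured maximum insertion depths will be calculated in Excel", then that "any differences between the conventional (VN) and the modified (VN+) groups will be determined with a Mann-Whitney test". The criterion is "A p-value<0.05 will be considered significant".

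No section defines overshoot in marks or names a depth that counts as deep. None plans an upper percentile, a share beyond a depth, or an effect estimate with an interval. Section 4 separately compares damage to tissue or organs between the needles with a t-test. That is a harm comparison and does not use depth.

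**The concern.** There are two gaps between the objective and the analysis. First, the objective is an amount, and a Mann-Whitney p-value is not one. Second, the test asks whether a VN insertion tends to be deeper than a VN+ insertion across the whole distribution. If injury is as rare as section 1 reports, it is reasonable to infer that the unusually deep passes matter most, although the documents do not say so. A needle that is shallower on most passes but still goes deep on some could win the rank comparison without any fall in deep passes. A report built on that p-value would then invite a conclusion about overshoot that the analysis had not tested, although the recorded depths could test it.

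**Working it through.** **1. The plan's own count.** Section 3.1 gives 3 groups of 10 and 5 attempts per device: 30 × 5 × 2 = 300 insertions, as section 3.2 states. That is 150 per needle, or 50 per needle within one experience group. There is no power calculation to reproduce.

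**2. Assumptions (none is in the documents).** Depth is lognormal with participant SD 0.15 and attempt SD 0.35 on the log scale, so the total SD is √(0.15² + 0.35²) = 0.381. The VN median is 25 mm. Ordinary VN+ passes have median 12, 20 or 22 mm. A share q of VN+ passes is replaced by values around 45 mm (log SD 0.10). Deep means over 40 mm.

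**3. Deep shares.** VN: 1 − Φ(ln(40/25)/0.381) = 10.9%. For VN+, a replaced pass is deep with probability Φ(ln(45/40)/0.10) = 88.1%. An ordinary pass is deep with probability 0.1%, 3.4% or 5.8% at medians 12, 20 and 22 mm. Example, 12 mm and q = 15%: 0.15 × 88.1% + 0.85 × 0.1% = 13.3%.

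**4. What the rank test sees.** It responds to θ, the probability that a random VN pass is deeper than a random VN+ pass. Against ordinary VN+ passes this is Φ(ln(25/median)/(0.381√2)) = 0.914, 0.661 and 0.594 at 12, 20 and 22 mm. Against replaced passes it is 1 − Φ(ln(45/25)/√(0.381² + 0.10²)) = 0.068. The two are mixed with weights 1 − q and q. With 150 per needle, the null SE of θ is √(301/(12 × 150²)) = 0.033, so a result favours VN+ once the estimate exceeds about 0.5 + 1.96 × 0.033 = 0.565.

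| Ordinary VN+ median | q | Deep share, VN v VN+ | θ | Simulated studies favouring VN+ |
|---|---|---|---|---|
| 12 mm | 12% | 10.9% v 10.6% | 0.81 | about 100% |
| 12 mm | 15% | 10.9% v 13.3% | 0.79 | about 100% |
| 12 mm | 20% | 10.9% v 17.7% | 0.74 | about 100% |
| 20 mm | 12% | 10.9% v 13.6% | 0.59 | 77% |
| 20 mm | 15% | 10.9% v 16.1% | 0.57 | 58% |
| 20 mm | 20% | 10.9% v 20.4% | 0.54 | 23–25% |
| 22 mm | 12% | 10.9% v 15.7% | 0.53 | 13% |
| 22 mm | 15% | 10.9% v 18.2% | 0.51 | 6% |
| 22 mm | 20% | 10.9% v 22.3% | 0.49 | 1% |

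Repeat runs differ by a few points. The simulated percentages follow θ: far above 0.565 the test nearly always favours VN+, and below it seldom does.

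**5. A second model.** Normal depths rounded to 0.5 SD marks, a separate deep stratum, 150 per needle, 4,000 runs per setting, attempts treated as independent as the planned test does. With the deep share equal at 10%, VN+ is favoured in 51.7%, 91.8% and 100% of runs for ordinary shifts of 0.3, 0.5 and 0.8 SD. With 5% (VN) v 10% (VN+), the figures are 27.9%, 78.9% and 99.8%. With 10% v 20%, they are 3.9%, 30.4% and 87.1%.

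**6. A milder failure mode.** If a failed VN+ pass simply behaves like a VN pass, with 12 to 30% failures and a 12 mm ordinary median, the VN+ deep share is 0.12 × 10.9% + 0.88 × 0.1% = 1.4%, up to 0.30 × 10.9% + 0.70 × 0.1% = 3.3%. Against 10.9% for VN, the tail improves along with the median.

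**7. The damage comparison as a backstop.** At the cited rates, 150 × 0.0023 = 0.35 and 150 × 0.0031 = 0.47 injuries are expected per needle. The chance of none in all 300 is 0.9977³⁰⁰ = 50% or 0.9969³⁰⁰ = 39%.

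**8. Precision of a tail comparison.** For 10% v 5% with 150 per needle, treated as independent samples: pooled SE √(0.075 × 0.925 × 2/150) = 0.0304; unpooled SE √((0.09 + 0.0475)/150) = 0.0303; power Φ((0.05 − 1.96 × 0.0304)/0.0303) = about 37%. For 10% v 2% it is 83.4%.

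**The case against.** The strongest reply is that the plan already looks at harm directly. Section 4 compares damage between needles, and the laparoscope in section 3.2 is there partly to see which structures are hit. A reader who inferred that the plan has no safety comparison would be wrong. But step 7 shows that at the clinical rates this comparison would usually have almost nothing to count. It is a real backstop only if damage in cadavers is much commoner, and the documents give no cadaver rate.

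Second, the adverse scenario is speculative. It needs 12 to 20% of VN+ passes to land far deeper than a typical VN pass. Nothing in the documents suggests that, and the decoupling mechanism in section 1 makes the milder failure in step 6 at least as natural. This stands: the documents give no ground for saying that the VN+ tail is worse, or that the study is likely to mislead.

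Third, a reader might infer that a rank test is all but blind to the tail. That is too strong. In the second model, raising the VN+ deep share from 10% to 20% against a VN share of 10% cuts favourable results from 91.8% to 30.4% at a 0.5 SD shift, and from 51.7% to 3.9% at 0.3 SD. Near-certain false reassurance belongs to a very large shift. Medians of 25 v 12 mm are ln(25/12)/0.381 = 1.9 SD apart.

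Fourth, the sentence in section 7, "If the VN+ really does make a significant difference in safety of VN insertion its use will lead to a worldwide reduction", is a conditional rationale for the work. It does not tie a safety claim to the Mann-Whitney p-value and should not be read as a decision rule.

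Finally, I take maximum depth to mean the maximum reached on each insertion. If it meant the deepest of each participant's five, the test would be closer to the tail but would still give no amount.

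**Conclusion.** The point holds as a cheap improvement. From the text alone, the planned depth analysis does not deliver the amount that section 2 asks for, and a significant result in favour of VN+ does not rule out an equal or larger share of deep insertions. The chance of such a result runs from about 1% to about 100% over the assumed settings. It depends mainly on how far ordinary depths shift and how many VN+ passes stay deep, and the documents give neither. That the deepest passes carry the harm is an inference from the overshoot rationale and the low cited injury rates. The calculations take little or no account of clustering by participant and cadaver. The planned test ignores it too, which is a separate matter.

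**What to change.** In section 4, add two depth summaries, both specified before the first insertion:

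1. The share of insertions beyond one fixed engraved mark, as the within-participant difference VN+ minus VN, with a 95% confidence interval.
2. The deepest of the five insertions per participant and needle, as a paired difference with a 95% confidence interval.

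Report both beside the rank test and the damage comparison, and state that the Mann-Whitney p-value alone will not support a claim of fewer deep overshoots. I would not add a rule that the claim stands whenever both summaries point towards VN+. In simulation with the 12 mm median, such a rule passed in about 46% of studies with equal tails and about 22% with a worse VN+ tail. The intervals should carry the judgement.

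The cost is a few lines of analysis on depths that are already recorded. One mark must be chosen in advance, and the tail estimates will be imprecise: about 37% power for 10% v 5% overall, and about 15% with 50 insertions per needle in one experience group. Only large reductions will show clearly, and the report should say so.

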## 3. Methods

### 3.1 Study design, population and procedures

Study design: open randomized controlled prospective cross over cohort study

Study population: A) group of 10 novices, B) group of 10 surgical, urological or gynaecological residents, C) group of 10 experts consisting of surgeons, urologists or gynaecologists.

Study procedure: After information is given on the purpose and set up of the experiment all participants will be asked to sign an informed consent form.

A video will be shown of the working of a normal VN and of the VN+. After this a detailed video will be shown wherein all basic steps of the procedure are outlined. Then after randomization half of the group will start with a VN and the other half with the VN+. After 5 attempts the groups will switch device and repeat the procedure.

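### The Student t-test planned for tissue and organ damage does not fit three experience groups and repeated, crossed-over insertions

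*Combined protocol and SAP*

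**What the plan says.** Section 4 (Data collection and analysis) gives one sentence to the analysis of damage: "All inadvertent tissue or organ damage will be determined and compared between the two types of needles and the groups using a Student T-test".

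Section 3.1 describes the design as an "open randomized controlled prospective cross over cohort study". Its population is "A) group of 10 novices, B) group of 10 surgical, urological or gynaecological residents, C) group of 10 experts". Each participant starts with one needle, and then: "After 5 attempts the groups will switch device and repeat the procedure". Section 3.2 gives the total: "As in total 300 VN(+) insertions have to be performed".

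Damage belongs to the secondary objectives in section 2: "Other secondary objectives are establishing the amount of haptic feedback of the VN+ compared to the standard VN and potential safety issues". The only injury rates in the document are the clinical ones in section 1: "incidences of Veress Needle (VN) injuries of e.g. 0.31% and 0.23" per cent.

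No section says whether damage is recorded as yes/no, a count or a grade, whether the unit is the insertion or the participant, or whether the test is paired. There is no rule for multiple comparisons.

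**The concern.** The named test does not fit the design in three ways.

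1. **Three groups.** A t-test handles two sets of values. Comparing novices, residents and experts with it means up to three pairwise tests, and nothing controls the overall error.
2. **Repeated, crossed data.** Each participant supplies 10 insertions, 5 per needle. A test on insertions treats one person's repeats as unrelated, so a few people who cause damage repeatedly can look like a difference between experience groups. An unpaired test also ignores that every participant uses both needles.
3. **Possibly very few events.** If damage is as rare as the clinical rates in section 1, there may be none. The t statistic is then undefined, and the plan offers nothing else to show how much harm the data still allow.

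At stake are a spurious experience effect on damage, a needle result that turns on an unstated choice of unit and pairing, and a non-significant p-value read as equal safety.

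**Working it through.** **Inputs from the document.** 3 groups x 10 participants and 5 insertions per needle (section 3.1); 300 insertions (section 3.2); significance at p < 0.05 (section 4, stated for insertion depth and assumed here to apply to damage, two-sided); clinical injury rates 0.23% and 0.31% (section 1).

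**Assumptions, because the document gives no figure.** Damage rate per insertion in cadavers: 2-20%, with the clinical rates treated separately. Within-participant correlation (ICC): 0 to 0.20.

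**Step 1: the plan's own figure.** 3 x 10 x 2 x 5 = 300, which agrees with section 3.2. That is 100 insertions per experience group and 150 per needle. Five attempts at each of the two entry sites would give 600, so 5 per needle is the reading that fits.

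**Step 2: three pairwise tests.** If the tests were independent, 1 - 0.95^3 = 14.3%. The pairs share groups, so the simulated figure is a little lower (step 3, ICC 0).

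**Step 3: experience groups.** Beta-binomial simulation with no true difference, 60,000 runs per setting, rates 2, 5, 10 and 20%. The design effect for 10 insertions per person is 1 + 9 x ICC: 1.45 at ICC 0.05, 1.9 at 0.10 and 2.8 at 0.20.

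| t-test run on | ICC | Type I error, one pair | At least one of three pairs |
|---|---|---|---|
| insertions (100 v 100) | 0 | 4-5% | 10-13% |
| insertions (100 v 100) | 0.05-0.20 | 8-25% | 18-48% |
| one value per participant (10 v 10) | 0-0.20 | 0.5-5% | 1-12% |

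**Step 4: needles, insertion level, 150 v 150.** Same rates, ICC 0.05-0.20, 100,000 runs per setting. Type I error is 2.5-4.5% if a participant's tendency to cause damage is the same with both needles (conservative, because pairing is ignored). It is 6.6-14.7% if the tendency is specific to participant and needle.

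**Step 5: the choice of unit can decide the result.** Suppose 4 events with VN and 0 with VN+.
- Insertion level: difference 4/150 = 0.0267; pooled variance 150 x 0.0267 x 0.9733 / 298 = 0.01306; SE = sqrt(0.01306 x 2/150) = 0.0132; t = 2.02 on 298 df; p = 0.044.
- Participant level, paired t on 30 differences with mean 4/30 = 0.133:
  - all 4 events from one participant: t = 1.00, p = 0.33;
  - 2 events from each of two participants: t = 1.44, p = 0.16;
  - 1 event from each of four participants: t = 2.11, p = 0.043.

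**Step 6: few or no events.** The chance of no event in 300 independent insertions is (1 - rate)^300: 50% at 0.23%, 39% at 0.31%, 4.9% at 1% and 0.2% at 2%. With no events, both means and the pooled variance are zero, so t = 0/0. With 0 of 150 on VN+, the exact 95% upper limit is 1 - 0.025^(1/150) = 2.4%, taking insertions as independent.

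Steps 3 and 6 are alternatives. At a rate of 0.31% the insertion-level chance of any false group difference is only about 0.1% at ICC 0 and 1-6% at ICC 0.05-0.20. At 2% or more, an event-free study is very unlikely.

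**The case against.** The strongest reply is that this is an under-specified secondary analysis, not a demonstrated error rate. The largest figures require an insertion-level test, which the plan never states, and a positive ICC, which no section gives. If damage were first reduced to one value per participant, a single pairwise test would not be inflated. The experience-group comparison of damage also appears only in section 4: section 2 links experience to overshoot and the learning curve, and its safety objective reads most naturally as VN+ against VN. For that needle contrast, inflation needs a tendency specific to participant and needle, for which the document gives no basis. Finally, the word groups is used loosely: section 4 also calls the VN and VN+ data groups, and section 3.1 uses the word for those who switch device.

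Much of this stands as a limit on the claim. The 18-48% is conditional, and for the needle comparison the direction of error is unknown. But section 4 opens by referring to all three groups, so experience groups is the natural reading. One value per participant would still leave three uncorrected pairwise tests, with up to about 12% overall error when damage is not rare, and the pairing would still be unstated. Step 5 shows that these unstated choices can decide significance. Nothing elsewhere in the document settles them.

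It is also fair to say that a participant-level analysis does not remove every dependence, since section 3.2 has two entry sites and probably three cadavers, and that a mixed model or GEE clustered on participant would be a reasonable alternative if events are frequent enough.

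**Conclusion.** The concern holds: the stated test is wrong for the stated design and should be fixed. For experience groups, three uncorrected t-tests give 10-13% overall error even with independent insertions, at assumed damage rates of 2-20%. An insertion-level analysis raises this to 18-48% at an assumed ICC of 0.05-0.20. For needles, no inflation is claimed if insertions are independent; with correlation the test may be conservative or liberal, depending on its source. If damage is as rare as the clinical rates in section 1, the chance of no event at all is 39-50%, and the planned test would then yield nothing. Cadaver damage, with novices operating, may well be more frequent, so this last point is secondary. Confidence is medium, because the unit of analysis is unstated and both the ICC and the cadaver damage rate are assumed.

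**What to change.** Replace the damage sentence in section 4 with a plan that does the following:

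- **Outcome.** Define tissue or organ damage and score each of the 300 insertions yes/no from the recordings; section 3.2 already provides for this: "The actions will all be filmed and photographed". List the structures injured descriptively, so that this detail is not lost.
- **Needles.** Take each participant's VN+ minus VN event count and apply a paired permutation (sign-flip) or sign test, n = 30.
- **Experience groups.** Run one three-group permutation test on participant totals, 10 per group, with pairwise tests only if it is significant.
- **Reporting.** Give event counts per needle and per group with exact 95% confidence intervals, and note that these ignore the repeats within participants. State that a non-significant result does not show equal safety. Tabulate events by entry site and cadaver.

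**Cost.** No extra insertions or filming are needed, only a written definition and the scoring time. Power is lower at small counts. A sign test needs at least 6 discordant participants, all in one direction, for p < 0.05 (2 x 0.5^5 = 0.0625; 2 x 0.5^6 = 0.031). In the example with four participants at one event each, it gives 2 x 0.5^4 = 0.125, against 0.043 from the paired t. The three-group permutation test is conservative when damage is rare: simulated size 1-2% at a 2% rate and 4-5% at 10-20%.
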